6.5.5. Ordinal Clinical Response at OAV#1 or OAV#2

If the subject died at any point of study participation, then OCR at OAV#1 will be 8.

Else if the subject has missing ACR at OAV#1 then OCR at OAV#1 will be missing.

Else if the subject did not have ACR at OAV#1 and was hospitalized from Day 1 to Day 5 then OCR at OAV#1 will be 7.

Else if the subject did not have ACR at OAV#1 and was not hospitalized from Day 1 to Day 5 then OCR at OAV#1 will be 6.

Else if the subject has missing resolution of symptoms at OAV#1 then OCR at OAV#1 will be missing.

Else if the subject did not have resolution of symptoms at OAV#1 then OCR at OAV#1 will be 5.

Else if the subject has missing most severe solicited event at OAV#1 then OCR at OAV#1 will be missing.

Else if the subject had a most severe solicited event of grade 3 at OAV#1 then OCR at OAV#1 will be 4.

Else if the subject had a most severe solicited event of grade 2 at OAV#1 then OCR at OAV#1 will be 3.

Else if the subject had a most severe solicited event of grade 1 at OAV#1 then OCR at OAV#1 will be 2.

Else OCR at OAV#1 will be 1.

If the subject died at any point of study participation, then OCR at OAV#2 will be 8.

Else if the subject has missing ACR at OAV#2 then OCR at OAV#2 will be missing.

Else if the subject did not have ACR at OAV#2 and was hospitalized from Day 1 to Day 18 then OCR at OAV#2 will be 7.

Else if the subject did not have ACR at OAV#2 and was not hospitalized from Day 1 to Day 18 then OCR at OAV#2 will be 6.

Else if the subject has missing resolution of symptoms at OAV#2 then OCR at OAV#2 will be missing.

Else if the subject did not have resolution of symptoms at OAV#2 then OCR at OAV#2 will be 5.

Else if the subject has missing most severe solicited event at OAV#2 then OCR at OAV#2 will be missing.

Else if the subject had a most severe solicited event of grade 3 at OAV#2 then OCR at OAV#2 will be 4.

Else if the subject had a most severe solicited event of grade 2 at OAV#2 then OCR at OAV#2 will be 3.

Else if the subject had a most severe solicited event of grade 1 at OAV#2 then OCR at OAV#2 will be 2.

Else OCR at OAV#2 will be 1.

Note that in some cases OCR can be defined even if some components are missing. For instance, if a subject had record of receipt of study product and did not have adequate clinical response at OAV#1, OCR at OAV#1 would still be defined even if most severe solicited event at OAV#1 was missing.

6.5.6. Number of Days of Antibiotic Use at OAV#1 or OAV#2

It will be assumed that all subjects have precisely five days of antibiotic use with the initial antibiotic prior to Day 1 (the day of the first dose of study product). Analysis involving comparisons of the number of days of antibiotic use will consider antibiotic use from Day 1 onwards. The number of days of antibiotic use is defined as the actual number of days of antibiotic use (any amount of study product that is not placebo, or any amount of other systemic antibiotic) from Day 1 to Day 5, inclusive, for OAV#1 and from Day 1 to Day 18 for OAV#2. For subjects that received placebo as study product, it is counted as the number of days of systemic antibiotic as determined solely from the concomitant medication form. For subjects that receive actual antibiotic as study product, it is counted as the number of days that the subject received any amount of either study product or a non-study systemic antibiotic, as determined

from the concomitant medication form. Note that missed doses of study product do not necessarily lower the number of days of antibiotic use as long as a separate dose of antibiotic (study product antibiotic or concomitant medication antibiotic) was received on that day. Extra doses of study product beyond the protocol specification of 10 doses count as normal toward the number of days of antibiotic use. The number of days of antibiotic use is missing (at both OAV#1 and OAV#2) if the product administration record was not completed / on record for the subject and the subject did not have antibiotic use during the study period recorded as a concomitant medication. If a subject does not have an OAV#1 or OAV#2, then number of days of antibiotic use at OAV#1 is missing. If a subject does not have an OAV#2, then number of days of antibiotic use at OAV#2 is missing. As exceptions, subjects that were hospitalized due to pneumonia or a complication of pneumonia or the died during the study period will have number of days of antibiotic use at OAV#1 or OAV#2 as 5 if randomized to the standard course or as 0 if randomized to short course if the number of days of antibiotic use at OAV#1 or OAV#2 is missing as defined above.

The number of days of antibiotic use at the time of analysis will be determined from the product administration records and concomitant medication records only. Data management activities and site queries (outside the scope of this document) prior to data lock will ensure concomitant medication records are as complete as possible and consistent with other records (i.e., AEs and medically attended visit records in the clinical database). The number of days of antibiotic use for a concomitant medication will be calculated as the medication end date minus the medication start date plus one day. Days will not be double counted if multiple systemic antibiotics (including antibiotic as study product) are taken on the same day. Systemic antibiotic use will not be counted for days that fall outside of the range being considered (Days 1 to Day 5, or Day 1 to Day 18).

If there is a start date but not an end date for a concomitant medication in the clinical database, then the end date for analysis will be imputed as follows. If the subject completed the study, then the end date for analysis will be reported as the protocol completion date. If the subject terminated early from the protocol and there is at least one other record for the same antibiotic in the concomitant medications records with start and end date known (record may belong to any subject), the end date of treatment for that antibiotic will be imputed by adding the mean observed number of days of treatment rounded up to the nearest integer for that antibiotic (minus 1). If no such records exist for the antibiotic and the subject terminated early, the end date of treatment for that antibiotic will be imputed by adding to the start date the mean observed number of days of treatment rounded up to the nearest integer for all systemic antibiotics in the concomitant medication records (minus 1).

6.5.7. Desirability of Outcome Ranking (DOOR) at OAV#1 or OAV#2

DOOR at OAV#1 is defined by ranking all subjects (pooling together both treatment arms) according to OCR at OAV#1 (lower is better) and using the number of days of antibiotic use at OAV#1 (lower is better) as a tie-breaker for comparing the ranking of two subjects with the same OCR. DOOR at OAV#2 is defined by ranking all subjects (pooling together both treatment arms) according to OCR at OAV#2 (lower is better) and using the number of days of antibiotic use at OAV#2 (lower is better) as a tie-breaker for comparing the ranking of two subjects with the same OCR. DOOR at OAV#1 or at OAV#2 is missing only if OCR or number of days of antibiotic use is missing for the respective OAV.

The ranking algorithm for DOOR is implemented as follows. A score variable is created that adds the number of days of antibiotic use (as defined in Section 6.5.6) divided by 100 to the OCR. Subjects are then ranked (DOOR) by the score, with the highest rank going to the subject with the lowest score, and the lowest rank going to the subject with the highest score. Tied scores result in a DOOR equal to the mean of the tied ranks. The algorithm is exemplified below using a simple scenario with 4 subjects.

Suppose Subject A has an OCR of 1 and 5 days of antibiotic use in the study period (score=1.05), Subject B has an OCR of 1 and 0 days of antibiotic use (score=1.00), Subject C has an OCR of 2 and 0 days of antibiotic use (score=2.00), and Subject D has an OCR of 1 and 5 days of antibiotic use (score=1.05). Because Subject B has the lowest score, Subject B is given DOOR=1 (the highest rank). Because Subject A and Subject D tie for the next lowest score, they both receive the mean of the next 2 available ranks (2 and 3, which has mean 2.5), and so the DOOR for both Subject A and Subject D is 2.5. Finally, Subject C has the highest score and therefore receives the worst available rank, which is DOOR=4.

6.6. Interim Analyses and Data Monitoring

One interim analysis, described below, will be performed by the SDCC statistician responsible for this protocol and reported to the DSMB after approximately 30% of the targeted subjects have completed the study. The interim analysis will inform DSMB decisions regarding stopping early for efficacy, futility, or safety. Only the SDCC statistician and the DSMB will see the interim analysis report.

For the interim analysis, a snapshot of the study database will be unblinded and used to conduct analyses as follows. An ITT analysis including all enrolled subjects in the snapshot of the study database will be performed, testing the null hypothesis (H_0 : Probability of higher DOOR in short course + $\frac{1}{2}$ probability of equal DOOR = 0.5) using the methods described in Section 8.1.1, with the modification that the Haybittle-Peto boundary ($p < 0.001$) will be used when concluding statistical significance. The study may be stopped early for efficacy only if statistical significance is detected in that test. In the event of statistical significance, sensitivity analyses using complete case and according-to-protocol cohorts (CC-V1 and ATP-V1, as described below) as well as worst case analyses will be included in the DSMB report to further guide decisions for stopping for efficacy.

A 95% confidence interval for the probability that a randomly selected subject will have a better DOOR if assigned to the 5-day strategy (vs. the standard strategy) will be estimated but not used to inform DSMB decisions about stopping early for efficacy. Predicted interval plots (PIPS, Section 6.6.1) will be constructed to provide the DSMB with a prediction of the trial results were the trial to continue as planned under varying assumptions regarding future data (e.g., current trend continues, null hypothesis is true, alternative hypothesis is true). In order to assess whether the 5-day strategy is differentially effective in subgroups of subjects, 95% confidence intervals for the probability of higher DOOR (as well as p-values for the test of a probability of higher DOOR of 0.5) when assigned to the short course of antibiotics will be shown as forest plots comparing each stratification variable (age < 2 years, age ≥ 2 years, ED as the initial treatment site, out-patient or urgent care as the initial treatment site, amoxicillin as the initial antibiotic, amoxicillin-clavulanate as initial antibiotic, and cefdinir as initial antibiotic).

The DSMB will also be provided with the following:

1. For subjects that have completed Outcome Assessment Visit #1 and have received at least one dose of study product, a between arm difference in the overall outcome (DOOR) via a cumulative difference plot with respective confidence bands for Outcome Assessment Visit #1.
2. For subjects that have completed Outcome Assessment Visit #1 and have received at least one dose of study product, a forest plot of 95% confidence intervals for the risk difference of adequate clinical response as well as the following interventions for persistent or worsening pneumonia: (1) ED/clinic visits, (2) hospitalizations, (3) surgical procedures, and (4) non-study systemic antibiotics at Outcome Assessment Visit #1.
3. For subjects that have completed Outcome Assessment Visit #1 and have received at least one dose of study product, a forest plot of 95% confidence intervals for the risk difference of lack of resolution of symptoms as well as the following: (1) Oral, rectal, axillary or tympanic temperature $\geq 38.3^{\circ}\text{C}$ (100.9°F), confirmed by repeat measurement after at least 15 minutes, in the 24 hours preceding Outcome Assessment Visit #1 or measured at the assessment visit, unless attributed to a new process that is unrelated to the prior diagnosis of pneumonia; (2) Elevated respiratory rate (RR >50 breaths/minute for children <24 months of age and >40 breaths/minute for children 24-71 months of age) at Outcome Assessment Visit #1, and (3) Presence of cough Grade 2 or 3 at Outcome Assessment Visit #1.
4. For subjects that have completed Outcome Assessment Visit #1 and have received at least one dose of study product, a forest plot of 95% confidence intervals for the risk difference of each solicited event and with the risk difference of any solicited event, for each severity threshold (mild or greater, moderate or greater, or severe) for Outcome Assessment Visit #1.

The Newcombe method with continuity correction will be used to compute all 95% confidence intervals for risk differences.

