11.3.1 Interim Analysis of Efficacy, Futility, and Safety

One interim analysis, described below, will be performed and reported to the DSMB after at least 30% of the targeted subjects have completed the study. The interim analysis will inform DSMB decisions regarding stopping early for efficacy, futility, or safety.

For the interim analysis, a snapshot of the study database will be unblinded and used to conduct analyses as follows. An ITT analysis including all enrolled subjects in the snapshot of the study database will be performed, testing the null hypothesis provided in Section 11.1 using the methods described in Section 11.4.1, with the modification that the Haybittle-Peto boundary ($p < 0.001$) will be used when concluding statistical significance. The study may be stopped early for efficacy only if statistical significance is detected in that test. In the event of statistical significance, sensitivity analyses using complete case and according-to-protocol cohorts (CC-V1 and ATP-V1, as described below) as well as worst case analyses will be included in the DSMB report to further guide decisions for stopping for efficacy.

A 95% confidence interval for the probability that a randomly selected subject will have a better DOOR if assigned to the 5-day strategy (vs. the standard strategy) will be estimated but not used to inform DSMB decisions about stopping early for efficacy. Predicted interval plots (PIPS)^{12,13} will be constructed to provide the DSMB with a prediction of the trial results were the trial to continue as planned under varying assumptions regarding future data (e.g., current trend continues, null hypothesis is true, alternative hypothesis is true).

The DSMB will also be provided with the following:

1. For subjects that have completed Outcome Assessment Visit #1 and have received at least one dose of study product, a between arm difference in the overall outcome (DOOR) via a cumulative difference plot with respective confidence bands for Outcome Assessment Visit #1
2. For subjects that have completed Outcome Assessment Visit #1 and have received at least one dose of study product, a forest plot of 95% confidence intervals for the risk difference of adequate clinical response as well as the following interventions for persistent or worsening pneumonia: (1) ED/clinic visits, (2) hospitalizations, (3) surgical procedures, and (4) non-study systemic antibiotics at Outcome Assessment Visit #1.

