6.3.1. Intention-to-Treat Analysis (ITT) Cohort

The ITT cohort will include all randomized subjects that were still eligible on Day 1 of the study. The analyses on the ITT cohort will be performed per randomized treatment assignment.

Randomized subjects who became ineligible before Day 1 of the study and did not take any study product will be excluded from ITT. Subjects randomized but not treated for other reasons other than ineligibility will be analyzed in the ITT cohort, but will have adequate clinical response and its components treated as missing. Therefore, in ITT analyses, OCR and DOOR will be missing and will need to be imputed for subjects that were not treated. If data (solicited events, cough, etc.) are collected post-randomization for a subject that was not treated, that data will be used in the ITT analysis to assist in imputing the OCR and DOOR.

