6.5.1. Adequate Clinical Response to OAV#1 or OAV#2

Subjects that have no record of receipt of at least one dose of study product will have adequate clinical response and its components considered missing at both OAV#1 and OAV#2. Otherwise, if a subject dies at any point during subject participation in the study, the subject will be considered as not having adequate clinical response at OAV#1 or OAV#2. Otherwise, if a subject does not have OAV#1 then ACR and its components are missing for OAV#1 and if a subject does not have OAV#2 then ACR and its components are missing for OAV#2.

Several variables are used to define the Adequate Clinical Response:

- MAVABRX: Was the subject prescribed or did the subject receive an additional antibiotic treatment at this visit? (Yes/No)
 - o MAVABCP: If Yes, was the antibiotic given for pneumonia or treatment for a complication of pneumonia? (Yes/No)
- MAVPLEUR: Drainage of pleural fluid as treatment for pneumonia or a complication of pneumonia? (Yes/No)
- MAVCHTB: Placement of a chest tube as treatment for pneumonia or a complication of pneumonia? (Yes/No)
- MAVVIDEO: Video assisted thoracoscopic surgery as treatment for pneumonia or a complication of pneumonia? (Yes/No)
- MAVTHOR: Thoracotomy procedure as treatment for pneumonia or a complication of pneumonia? (Yes/No)
- MAVSURG: Any other surgical procedure as treatment for pneumonia or a complication of pneumonia? (Yes/No)
- MAVHOSP: Was the subject hospitalized at this visit? (Yes/No)
 - o MAVHPPN: If Yes, was the hospitalization for the treatment of pneumonia or pneumonia complications? (Yes/No)

If a subject has OAV#1 and did not have a medically attended visit (MAV) from Day 1 to Day 5, inclusive, then the subject had adequate clinical response for OAV#1. If the subject had a MAV from Day 1 to Day 5 for which MAVABRX and MAVABCP were both YES (receipt of a non-

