8.2.2.5. Worst Case Analysis of the DOOR at Outcome Assessment Visit #1

Analysis will be performed as described in Section 8.2.2 using the ITT population with missing values imputed as follows. Subjects in the short course arm will have their ordinal clinical response imputed as 8 and their number of days of antibiotic use imputed if missing (see Section 6.5.6) as 0. As an exception, subjects in the short course arm with OCR missing for Outcome Assessment Visit #1 but not for Outcome Assessment Visit #2 will have the OCR for Outcome Assessment Visit #1 imputed as the Outcome Assessment Visit #2 value or as 5, whichever value is larger. Subjects in the standard course arm will have their ordinal clinical response imputed as the value that would occur if all missing data was benign (no additional solicited events / cough / fever, etc.) and their number of days of antibiotic use imputed if missing (see Section 6.5.6) as 5.

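### The interim ITT set takes in children whose OAV#1 is not yet due, so the worst-case analysis sent to the DSMB partly reflects recent accrual and not only loss to follow-up

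*SAP*

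**What the plan says.** SAP 6.6 triggers the interim by completers: it is "reported to the DSMB after approximately 30% of the targeted subjects have completed the study". Protocol 11.3.1 (Interim Analysis of Efficacy, Futility, and Safety) has "after at least 30% of the targeted subjects have completed the study". Neither pauses enrolment. The set analysed is wider than the completers: "An ITT analysis including all enrolled subjects in the snapshot of the study database will be performed". The general ITT definition in SAP 6.3.1 adds no visit condition either: "The ITT cohort will include all randomized subjects that were still eligible on Day 1 of the study".

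The missing-data rules do not separate a visit not yet due from a visit missed. Under SAP 6.5.1, "if a subject does not have OAV#1 then ACR and its components are missing for OAV#1". SAP 6.5.5 and 6.5.6 then make the ordinal clinical response (OCR) and the antibiotic days missing, so DOOR is missing.

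The interim test uses the "Haybittle-Peto boundary" of p<0.001. If it is crossed, complete-case and according-to-protocol results "as well as worst case analyses will be included in the DSMB report to further guide decisions for stopping for efficacy". The DOOR worst-case rule for this visit is in SAP 8.2.2.5: "Subjects in the short course arm will have their ordinal clinical response imputed as 8", with antibiotic days set to 0 if missing. Missing standard-arm data are taken as benign, with 5 days. The one exception needs an OAV#2 value.

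**The concern.** A child enrolled last week has no OAV#1 outcome because the visit is not due, which says nothing about retention. The interim rules treat that child like one lost to follow-up, with two effects.

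In the stopping test and the predicted interval plots, such children are filled in by the imputation model. The memory aid is reviewed at OAV#1 (protocol 7.3), so before that visit the model has little beyond site, strata and treatment. The test gains imputed values and no outcomes. In the plots (SAP 6.6.1), pending children follow the fitted model even under the null and alternative scenarios, although they logically belong with the future subjects.

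In the worst-case analysis, pending short-arm children take OCR 8, the category for death, and cannot meet the OAV#2 exception. An analysis meant to show robustness to dropout then varies with how fast the trial was enrolling just before the data cut.

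The four other DSMB outputs listed in SAP 6.6 are limited to children who completed OAV#1. The ITT test and the analyses built on it have no comparable limit.

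**Working it through.** **Plan's own figures.** The plan gives no number for pending children or for the size of the interim ITT set. The nearest figure is the sample size. Noether's formula in SAP 5 gives (1.960 + 1.282)² / [12 × 0.25 × 0.1²] = 350.2, against 360 stated; 360/0.90 = 400 matches the enrolment target used below.

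**1. Time from enrolment to OAV#1.** Enrolment is on Day -3 to Day 1 and the visit on Day 6 to 10 (protocol 4; SAP 4.1). There is no Day 0. Shortest: Day 1 to Day 6, 5 days. Longest: Day -3 to Day 10, 12 days.

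**2. Children pending at a snapshot.** 400 over 24 months is 400/(24 × 30.4) = 0.55 per day. Uniform accrual is my assumption.
- Uniform: 2.7 to 6.6 in total, about 1 to 3 in the short arm.
- Two-fold rate (assumed): 5.5 to 13.2.
- Three-fold rate (assumed): 8.2 to 19.7.

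**3. Children assessed.** 30% of 400 is 120 completers. Children between the two visits (Day 8 to Day 22, 14 days) add 7.7 at the uniform rate, 15.4 at two-fold and 23.0 at three-fold. That gives about 128, 136 and 143; 127 is used for the case with 3 pending.

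**4. Index at the boundary.** With a assessed per arm and the no-ties null variance given under SAP Table 16, the index at two-sided p = 0.001 is θ = 0.5 + 3.29 × √[(2a + 1)/(12a²)]. For a = 64: 0.5 + 3.29 × 0.0512 = 0.669.

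**5. Worst-case index with k pending per arm.** Pending short-arm children lose every comparison. Pending standard-arm children score 1.05 (OCR 1, 5 days), so an assessed short-arm child beats them only with OCR 1 and fewer than 5 antibiotic days. Let q be the proportion of short-arm children like that, assumed 40% to 70%. Then

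θ_wc = (a²θ + a·k·q)/(a + k)².

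Example with 7 pending, a = 64, k = 3.5, q = 0.40: (4096 × 0.669 + 64 × 3.5 × 0.40)/67.5² = 0.621, z = 2.42, p = 0.016.

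| Pending, total | Assessed | Index at p = 0.001 | Worst-case index | Worst-case p |
|---|---|---|---|---|
| 3 | 127 | 0.669 | 0.648–0.654 | 0.002–0.004 |
| 7 | 128 | 0.669 | 0.621–0.635 | 0.007–0.016 |
| 13 | 136 | 0.664 | 0.585–0.609 | 0.02–0.07 |
| 20 | 143 | 0.659 | 0.551–0.583 | 0.07–0.26 |

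True dropouts are set to zero, so the table isolates the effect of pending children.

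**6. A result well past the boundary.** Take 60 assessed per arm, index 0.76 and q = 0.70. Two pending per arm give (3600 × 0.76 + 60 × 2 × 0.70)/62² = 0.73. Three give (3600 × 0.76 + 60 × 3 × 0.70)/63² = 0.72. Both keep p below 0.0001.

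**The case against.** The case for leaving the text alone is substantial.

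- The worst-case analysis appears only after p<0.001, and it guides the decision without being a stopping rule. A reader might infer that a moderate interim result could be dragged to one half or below. The documents do not support that. With 60 assessed per arm the boundary index is 0.5 + 3.29 × √[121/(12 × 3600)] = 0.674; an index of 0.66 (p about 0.0025) or 0.61 (p about 0.04) would never produce a worst-case analysis.
- A reader might infer that the stopping test itself counts pending children as deaths. It does not: it imputes under missing-at-random (SAP 6.5), and the between-imputation term in SAP 8.1.1 reflects the missing information. OCR 8 is the plan's deliberate extreme value, used only in the worst case.
- A reader might infer a threat to type I error. The worst-case shift runs against the short course, so it can only discourage stopping on a result in that arm's favour.
- The same DSMB report carries CC-V1 and ATP-V1, which exclude anyone without an unambiguous OAV#1 DOOR.
- Scheduled DSMB reviews follow each respiratory season (protocol 9.6.1). If the interim is cut then, accrual should be low. The documents do not tie the interim to that date, so the peak case is possible but not the expected one.

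All of this limits the size of the point. None of it supplies a rule for visits not yet due.

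**Conclusion.** The point holds as a minor flaw in a stated rule. Read literally, SAP 6.6 and protocol 11.3.1 place not-yet-due children in the interim ITT set, and SAP 8.2.2.5 then makes a DSMB stopping aid depend partly on accrual at the cut.

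At uniform accrual about 3 to 7 children in total are affected. For a result exactly at the boundary, that is enough to move the worst-case p from 0.001 to between 0.002 and 0.016. At an assumed three-fold peak, with up to about 20 pending, the worst-case p could reach 0.07 to 0.26. A result well past the boundary keeps its conclusion at planned accrual. The sizes rest on even enrolment, the no-ties variance, no true dropouts and the assumed 40% to 70% for q; the reading of the text does not.

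A related gap has the same cause: a child enrolled before Day 1 cannot yet be checked against the Day 1 eligibility condition in SAP 6.3.1.

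**What to change.** In SAP 6.6 and protocol 11.3.1, limit three things to randomized children whose OAV#1 window (Day 10) has closed by the snapshot date: the interim ITT test, its worst-case analysis, and the interim set carried into the predicted interval plots. Impute only true missingness among them. In SAP 6.6.1, count pending children among the future subjects.

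The condition should be a closed window, not attendance, so that real dropouts stay in and early attenders are not favoured. It can be applied to every child, because SAP 3.3 defines Day 1 even when no study product is recorded. It also settles the Day 1 eligibility question.

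The cost is small. From enrolment to Day 10 takes 9 to 12 days, so at 0.55 per day about 5 to 7 children leave the interim set, most of them without an OAV#1 outcome. The protocol wording must change with the SAP; otherwise SAP 13, which now reports no changes to the planned analyses, must record the departure. The same edit can align the 30% trigger, which the SAP calls approximate and the protocol a minimum.

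One case remains. A short-arm child who missed OAV#1 and is not yet due for OAV#2 would still score 8 at the interim, though the final analysis could use the larger of the OAV#2 value and 5. A note in the DSMB report would be enough.
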